1.0 Research Design

1.1 Purpose/Specific Aims

The purpose of the proposed study is to compare the effectiveness of video instructions versus a patient handout as method for patient comprehension and opioid usage for meniscectomy patients.

A. Objectives

The primary objective is to compare the effectiveness of video instructions versus a patient handout as method for patient comprehension of concept areas such as how to care for the incision, how to safely manage pain with and without opioids, the side effects of opioids. The secondary objective is to evaluate whether the utilization of video instructions versus a patient handout will lead to lower post-operative use of opioid medications.

B. Hypotheses / Research Question(s)

The use of video for pre-operative education for meniscectomy surgery will improve patient comprehension of operative instructions compared to paper handout. Secondly, the use of video will help to minimize opioid usage post-operatively.

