Day of Surgery: All patients will be receiving the same preoperative care, undergo meniscectomy via the same surgical technique, and same postoperative care in the post-anesthesia care unit (PACU) after surgery. In the PACU, patients in the control group will again be given a physical copy of the handout of operative guidelines. Likewise, patients in the study group will also be sent a link by email, again in the PACU after surgery.

After surgery: At the first postoperative visit, 10 to 14 days after surgery, patients will be given a questionnaire to evaluate their comprehension of concepts which were outlined in the video or the handout. The questionnaire will consist of 12 multiple choice questions with concepts including areas such as how to care for the incision, how to safely manage pain with and without opioids, the side effects of opioids (Questionnaire in supplemental section of eIRB). Patients will also be asked to rate how helpful they found the information in the assigned instructions on a scale of 1 to 5 (1 = not at all helpful, 5 = extremely helpful), how many times they viewed the instructions, and at what time point the instructions were most helpful to read (before the procedure, at the surgical center, or after the procedure). Lastly, patients will be asked to report the number of opioid and other analgesic medications they took following surgery.

B. Data Points

Age, injury type, surgery performed, use of narcotic and other analgesic pain medication, number of times instructions viewed or read

C. Study Duration

The study will be conducted from time of IRB approval until the minimum number of participants shown below have completed the study. Each subject will participate in the study from their pre-operative appointment until 14 days after surgery.

D. Endpoints

Primary endpoints: The number of questions answered correctly, and patient-reported helpfulness of the material, on a scale of 1-5 to detect clinically significant difference in patient comprehension.

Secondary endpoint: Number of opioid and other analgesic medications taken

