1.9 Data Collection

A. Primary Data Collection

B.

- **Location**: Data will be collected via online survey/questionnaire utilizing RedCAP
- **Process of Data Collection**: Patients will be educated on how to access the online survey and a research assistant will ensure patient access.
- **Timing and Frequency**: The survey will be accessible to patients at their first post-operative visit, day 10-14.
- **Procedures for Audio/Visual Recording**: *N/a*
- **Study Instruments**: Qualitative data will be collected via a questionnaire created by the researchers.
- **Ethnographic Studies, Interviews, Or Observation**: Patients will be provided with questionnaires via the app/web based system including pain scores, number of narcotic and non-narcotic pain medications used, as well as any adverse events.
- **Subject Identifiers**: Patient data will not include any identifiers.

C. Secondary Data Collection

Not Applicable

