6.0 Data Management Plan

6.1 Data Analysis

Data will be analyzed by the statisticians. Statistical comparisons will be made between patients receiving paper instructions vs. video instructions. The mean number of questions answered correctly for both the groups were compared using the student t-test. For secondary variables and baseline characteristics, statistical testing was performed based on the type of variable: the chi-square test for categorical variables and the student t-test (parametric) or Mann-Whitney U test (nonparametric) for continuous variables. For the ordinal variable of patient-reported helpfulness, the Mann-Whitney U test was used.

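### The secondary objective is lower opioid use, but the only secondary endpoint names opioids and other analgesics together, with no opioid-only outcome and no unit

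*Protocol*

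**What the plan says.** Section 1.1 states the secondary objective as whether video rather than a handout "will lead to lower post-operative use of opioid medications". The matching hypothesis is that "the use of video will help to minimize opioid usage post-operatively". Both are about opioids only. Section 1.2 gives the same motive: it notes that the earlier handout-versus-video study did not count opioids in its two groups.

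Section 1.3 D then gives one line: "Secondary endpoint: Number of opioid and other analgesic medications taken". No other secondary endpoint is listed. Section 1.6 lists only the two primary outcomes as dependent variables, so it does not clarify the matter.

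The data come from patient report. Section 1.3 A says "Lastly, patients will be asked to report the number of opioid and other analgesic medications they took following surgery", at the first postoperative visit on day 10 to 14. Section 1.9 describes questionnaires "including pain scores, number of narcotic and non-narcotic pain medications used, as well as any adverse events". Section 6.1 does not name opioid use; it covers secondary variables by a general rule based on variable type.

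**The concern.** The endpoint does not match the question it is meant to answer, in three respects.

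- **Which drugs.** The objective asks about opioids, while the endpoint line covers opioids and everything else taken for pain. If the two are added, variation in non-opioid use is noise for the opioid question. The instructions and the questionnaire deal with managing pain both with opioids and without them. A patient who understands them better might take fewer opioids and more non-opioids, and in a total these changes offset each other.
- **Which unit.** A number of medications could be tablets, doses or distinct drugs. These are different outcomes and can give different answers.
- **Which strength.** A raw count gives a weak and a strong opioid tablet the same weight, even if only opioids are counted.

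At stake is one of the trial's two hypotheses. A real opioid reduction could be reported as no effect, or a change in non-opioid use could be presented as an opioid result. Because the line allows more than one reading, the pooled or the opioid-only result could be chosen after the data are seen. Section 7.0 says that data are deleted when the study is complete, so detail that is not collected, or not kept by class, may not be recoverable.

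**Working it through.** **Step 1: the texts side by side.**

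| Place in protocol | Drugs named | Unit | Opioids defined as a separate outcome? |
|---|---|---|---|
| 1.1 objective and hypothesis | Opioids | None | Opioids are the only subject |
| 1.3 D endpoint | Opioids and other analgesics | Number of medications | No |
| 1.3 A questionnaire | Opioids and other analgesics | Number of medications | Not stated |
| 1.9 data collection | Narcotic and non-narcotic | Number used | Possibly recorded by class; analysis not stated |

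No section says the classes are summed, and none says opioids are analysed alone. The mismatch between 1.1 and 1.3 D needs no arithmetic.

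**Step 2: the plan's own sample-size figures.** Section 1.5 gives no figure for the secondary endpoint. Its table does reproduce. A two-sample t-test at two-sided 0.05 and power 0.80 needs 64, 45, 34 and 26 per arm for effects of 0.50, 0.60, 0.70 and 0.80 SD. Dividing by (1 − 0.20) and rounding up gives 80, 57, 43 and 33. Both rows agree with the table and are not in dispute.

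**Step 3: what pooling would cost, if it is done.** All inputs here are assumptions except the 64 per arm, which is the first row of the 1.5 table. It is also the upper end of the 4.3 target after 20% loss: 160 × 0.8 / 2 = 64.

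- True opioid-only effect: 0.50 SD of the opioid count.
- Non-opioid SD: k times the opioid SD, with k = 1 or 2.
- Correlation between the two counts: r = −0.3, 0 or +0.3.
- Fraction of avoided opioid units replaced one for one by non-opioids: f = 0, 0.5 or 1.

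SD of the total, in opioid SDs: √(1 + k² + 2rk). 
Effect on the total: δ = 0.50 × (1 − f) / √(1 + k² + 2rk). 
Power: Φ(δ√(n/2) − 1.96), with n = 64, so √(n/2) = 5.657.

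Opioids alone: 0.50 × 5.657 − 1.96 = 0.87, giving power of about 0.80. 
Pooled, k = 1, r = −0.3, f = 0: δ = 0.50 / √1.4 = 0.423; 0.423 × 5.657 − 1.96 = 0.43, giving power 0.67. 
Pooled, k = 2, r = +0.3, f = 0: δ = 0.50 / √6.2 = 0.201; 0.201 × 5.657 − 1.96 = −0.82, giving power 0.21.

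| k | r | δ, f = 0 | Power, f = 0 | δ, f = 0.5 | Power, f = 0.5 |
|---|---|---|---|---|---|
| 1 | −0.3 | 0.423 | 0.667 | 0.211 | 0.222 |
| 1 | 0 | 0.354 | 0.516 | 0.177 | 0.169 |
| 1 | +0.3 | 0.310 | 0.418 | 0.155 | 0.139 |
| 2 | −0.3 | 0.256 | 0.305 | 0.128 | 0.109 |
| 2 | 0 | 0.224 | 0.244 | 0.112 | 0.092 |
| 2 | +0.3 | 0.201 | 0.205 | 0.100 | 0.082 |

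With f = 1 the effect on the total is zero by construction, so that row carries no further information.

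**The case against.** The strongest reply is that pooling is nowhere stated. The endpoint line can be read as two counts, 1.9 names narcotic and non-narcotic medications as two kinds, and 1.2 shows that an opioid count is what the investigators want. This stands. A reader might infer that the trial adds the classes and so cannot answer its opioid question; the protocol does not support that. If counts are kept by class, an opioid-only comparison remains possible. The defect that remains is that no such outcome is defined. The power figures describe one reading, and their size depends on assumed spread and correlation.

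Four further inferences are tempting and not supported.

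- That the video teaches substitution. Section 1.3 A says both arms receive the same content, pain management included. A difference between arms would have to come from better comprehension.
- That the choice of test inflates the error rate. Section 6.1 offers "the student t-test (parametric) or Mann-Whitney U test (nonparametric) for continuous variables" according to variable type. It does not say that both are run and the smaller p-value kept, and the final test for a secondary endpoint may properly sit in the SAP.
- That the day 10 to 14 visit window undermines the count. The period can differ by up to 40% between two patients (14/10 = 1.4), but nothing makes it differ by arm. With visits spread evenly over the five days and constant daily use (both assumed), the coefficient of variation of the total rises only from 0.50 to 0.52.
- That asking about medication last, after the opioid questions, invites under-reporting. The form is not shown, the order in the text may be narrative only, and both arms answer the same questions.

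It is also fair to say that the form may already capture product and strength, and that a tablet count is not in itself an error. Neither point supplies the missing definition. An SAP can choose the model, but the protocol should say which drugs the endpoint counts and in what unit.

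**Conclusion.** The concern holds as a mismatch and a gap in definition. The secondary objective and hypothesis are about opioids alone; the sole secondary endpoint defines neither an opioid-only outcome nor a unit, and a raw count cannot equate opioids of different strength. That conclusion rests on the text only.

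The size is conditional. If the classes were pooled, with a 0.50 SD opioid effect, 64 per arm and the assumed spreads and correlations, power would fall from about 0.80 to between 0.67 and 0.21 without substitution. It would fall to between 0.22 and 0.08 if half the avoided opioids were replaced. If the classes are analysed separately, this loss does not arise, and the missing unit and the unequal strengths remain.

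Severity is moderate. The primary comparison and the sample-size table are untouched.

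**What to change.** Replace the line in 1.3 D with an opioid-only definition, and align 1.3 A, 1.6 and 1.9 with it:

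- **Secondary endpoint:** total opioid consumption, in morphine-equivalent units, from surgery to the first postoperative visit.
- **Data:** record the product and strength with each count, and the day of the visit so that the period covered is known for every patient.
- **Separate outcome:** non-opioid analgesic use, reported on its own and not added to the opioid figure.
- **Context:** report the pain scores already listed in 1.9 beside both, so that lower opioid use can be read together with pain control.

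Keeping the period up to the visit avoids asking a patient seen on day 14 to recall use only to an earlier cut-off.

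The cost is revised endpoint wording, one extra survey field for product and strength (if the form lacks it), the visit day, and a conversion table fixed before analysis. The sample size does not change.

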1.4 Preliminary Data

There is currently no relevant preliminary data collected at University Orthopaedic Associates.

1.5 Sample Size Justification

PG Power Table			Primary 2 Arm Treatment Comparison		Primary 2 Arm Treatment + Anesthesia Subgroup Comparison	
Statistical Significance	Power	Desired Effect Size	N per Treatment Type (2 Groups) 0% Drop-Out Inflation	N per Treatment Type (2 Groups) 20% Drop-Out Inflation	N per Treatment Type (4 Groups) 0% Drop-Out Inflation	N per Treatment Type (4 Groups) 20% Drop-Out Inflation
0.05	0.80	0.50 (medium)	64	80	128	160
0.05	0.80	0.60 (medium)	45	57	90	114
0.05	0.80	0.70 (medium)	34	43	68	86
0.05	0.80	0.80 (large)	26	33	52	66

1.6 Study Variables

A. Independent Variables, Interventions, or Predictor Variables

Independent Variable: video containing operative instructions

B. Dependent Variables or Outcome Measures

Dependent Variable: number of questions answered correctly, and patient-reported helpfulness of the material, on a scale of 1-5 at the first post-operative visit (day 10-14)

1.7 Drugs/Devices/Biologics

A. Schedule and Administration

Patients in the control group will be given a physical copy of the handout of operative guidelines at the time they book their surgery in the office, and again in the post-anesthesia care unit (PACU) after surgery. Those in the study group will receive a link at the same time-points by email, when they book their surgery in the office and again in the PACU after surgery, which provides access to a video on YouTube outlining the same operative instructions.

B. Drug/Device Accountability and Storage Methods

Not Applicable

1.8 Specimen Collection

A. Primary Specimen Collection

Not Applicable

B. Secondary Specimen Collection

Not Applicable

1.9 Data Collection

A. Primary Data Collection

B.

- **Location**: Data will be collected via online survey/questionnaire utilizing RedCAP
- **Process of Data Collection**: Patients will be educated on how to access the online survey and a research assistant will ensure patient access.
- **Timing and Frequency**: The survey will be accessible to patients at their first post-operative visit, day 10-14.
- **Procedures for Audio/Visual Recording**: *N/a*
- **Study Instruments**: Qualitative data will be collected via a questionnaire created by the researchers.
- **Ethnographic Studies, Interviews, Or Observation**: Patients will be provided with questionnaires via the app/web based system including pain scores, number of narcotic and non-narcotic pain medications used, as well as any adverse events.
- **Subject Identifiers**: Patient data will not include any identifiers.

C. Secondary Data Collection

Not Applicable

1.10 Timetable/Schedule of Events

This study will have two groups that will each go through the timetable below. Patients will receive operative instructions at the first preoperative clinic visit when they book their procedure. Patients in the control group will be given a physical copy of the handout of operative guidelines at the time they booked their surgery in the office, and again in the post-anesthesia care unit (PACU) after surgery. Those in the study group will receive a link at the same time-points by email, when they booked their surgery in the office and again in the PACU after surgery, which provided access to a video on YouTube outlining the same operative instructions. At the first postoperative visit, 10 to 14 days after surgery, patients will be given a questionnaire to evaluate their comprehension of concepts which were outlined in the video or the handout.

2.2 Research Staff Training

Research Staff Training: All research staff has successfully completed CITI Training (Collaborative Institutional Training Initiative).

2.3 Other Resources

Facilities: The research will be conducted at University Orthopaedic Associates, LLC (UOA). Medical or Psychological Resources: Medical treatment related to orthopaedics can be provided by the study physicians. Other required medical care can be referred to the appropriate clinician. Psychological assistance can be referred to an appropriate mental health professional.

4.0 Subject Considerations

4.1 Subject Selection and Enrollment Considerations

A. Method to Identify Potential Subjects

Patients 18 or older, undergoing a meniscectomy procedure at University Center for Ambulatory Surgery, LLC (UOA) will be reviewed for eligibility.

B. Recruitment Details

Recruitment will take place at the UOA office during patient visits. Patients will be provided with educational pamphlet. Recruitment will take place by study staff.

C. Subject Screening

Subjects will be screened by attending physicians in the office setting as patients are being indicated for surgery as per standard of care.

▪ Inclusion Criteria

- Patients 18 or older
- Undergoing a meniscectomy procedure
- English speaking
- Intact decision-making capacity
- Have access to the required technology to participate in this study (cell phone to receive text messages and view the instructional video)

▪ Exclusion Criteria

- Patients who did not speak English
- Patients with documented cognitive impairment or neurological disorder affecting word processing or memory
- Patients who do not have access to a cell phone to view the video

D. Privacy Protections

Data collected via an online questionnaire that is protected by HIPPA regulations. Data will be de-identified prior to statistical analysis.

4.2 Obtaining Identifiable Information About Non-Subjects

N/A

4.3 Number of Subjects

A. Total Number of Subjects

80-160 patients targeted to be recruited to account for study dropout

B. Total Number of Subjects If Multicenter Study

N/a

C. Feasibility

University Orthopaedic Associates is a high-volume orthopaedic center. Physicians including Drs. [name], [name], [name], and [name] see a high volume of patients undergoing meniscectomy and it is therefore reasonable to accrue the required number of patients to achieve statistical significance for this study.

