1.3 Research Design and Methods

This is a single-blinded prospective randomized controlled clinical trial. Patients 18 or older, undergoing a meniscectomy procedure at University Center for Ambulatory Surgery, LLC (UOA), who are English speaking, with intact decision-making capacity, and have access to the required technology to participate in this study (cell phone to receive text messages and view the instructional video), will be reviewed for eligibility. Patients who did not speak English and/or had documented cognitive impairment or neurological disorder affecting word processing or memory will be excluded from the study. Once identified, potential study subjects will be asked whether they are interested in participating in the project. If the patient agrees, the subject will be given the informed consent to read and sign.

A. Research Procedures

Preoperative Visit: All patients who consent will have operative instructions explained by the study surgeon and his assistants. Patients will then be allocated to either the video or handout group with the use of a computer-generated block randomization sequence, with the study surgeon blinded to patient allocation. Due to the nature of the material provided, it is not possible to blind the patients to the allocation. Patients in the control group will be given a physical copy of the handout of operative guidelines at the time they book their surgery in the office. Those in the study group will receive a link at the same time point when they book their surgery in the office, via email, which will provide access to a video on YouTube outlining the same operative instructions. A research assistant will confirm patients in the study group receive the video by email and that the link was playable/ accessible to them.

Patients in both groups will be aware that they would be asked questions regarding the contents of the instructions. Patients had unlimited access to the video once they were provided the link. The

video was less than 10 minutes long, and it was accessible by computer, tablet, or cell phone. The content of the video and paper handout mirrored each other and consisted of general operative instructions, incision and dressing care, symptom monitoring, and pain management (Video 1, Appendix 1).

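### The total recruitment target of 80-160 appears to reuse per-arm figures from the power table; its lower end falls short of three of the table's four rows, and no single sample size is fixed

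*Protocol*

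**What the plan says.** Three places in the Protocol bear on the sample size.

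- **Section 1.5** is a table with four effect sizes (0.50, 0.60, 0.70, 0.80) at significance 0.05 and power 0.80. All its sample-size columns are per treatment type. The two-arm columns are "N per Treatment Type (2 Groups) 0% Drop-Out Inflation" and "N per Treatment Type (2 Groups) 20% Drop-Out Inflation". A second pair, under "Primary 2 Arm Treatment + Anesthesia Subgroup Comparison", ends with "N per Treatment Type (4 Groups) 20% Drop-Out Inflation". The first row reads "0.05 0.80 0.50 (medium) 64 80 128 160". No row or column is marked as the one adopted.
- **Section 4.3 A**, headed as the total number of subjects, gives "80-160 patients targeted to be recruited to account for study dropout".
- **Section 1.3 C** keeps the study open "until the minimum number of participants shown below have completed the study".

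The design has two arms: "Patients will then be allocated to either the video or handout group with the use of a computer-generated block randomization sequence" (Section 1.3 A). Section 6.1 compares the mean number of correct answers between the arms with a Student t-test.

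**The concern.** The two ends of the range in Section 4.3 are the two dropout-inflated cells of the d = 0.50 row in Section 1.5. There they are counts per treatment type; in Section 4.3 they are a total for the whole trial. If the lower end is a per-arm figure read as a total, a team that stops at 80 complies with the protocol while recruiting half of what that row requires for two arms.

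The completion rule does not resolve this. It refers to a minimum shown below, and what follows is a table of four effects and four columns with no choice made, then a twofold range. Section 4.3 C calls it feasible to accrue the required number, but no required number is identified. What is at stake is whether the 80% power in the table applies to the trial that will actually be run.

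**Working it through.** **Inputs.** Significance 0.05, power 0.80, d = 0.50 to 0.80 and 20% dropout come from Section 1.5; the t-test from Section 6.1; two arms from Section 1.3 A; the total of 80-160 from Section 4.3 A. Two inputs are not stated and are assumed: a two-sided test and 1:1 allocation.

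**Step 1: reproduce the table.** For n per arm, the two-sample t-test has noncentrality d × √(n/2) on 2n − 2 degrees of freedom. Solve for 80% power, round up, then divide by 1 − 0.20 and round up again.

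| d | n per arm, computed | rounded up | ÷ 0.80 | rounded up | table |
|---|---|---|---|---|---|
| 0.50 | 63.8 | 64 | 80.0 | 80 | 64 / 80 |
| 0.60 | 44.6 | 45 | 56.25 | 57 | 45 / 57 |
| 0.70 | 33.02 | 34 | 42.5 | 43 | 34 / 43 |
| 0.80 | 25.5 | 26 | 32.5 | 33 | 26 / 33 |

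All four two-arm rows match exactly. A one-sided test would need 50.2 per arm at d = 0.50, which does not match, so the two-sided assumption is well supported. Because the table gives one number per treatment type, equal allocation is too.

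**Step 2: totals for two arms, with dropout.** 2 × 80 = 160, 2 × 57 = 114, 2 × 43 = 86 and 2 × 33 = 66. A total of 80 equals none of these. It lies below the totals for d = 0.50, 0.60 and 0.70, and above that for d = 0.80.

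**Step 3: power at each end of the range.** A total of 80 is 40 per arm, and 40 × 0.80 = 32 evaluable. A total of 160 is 80 per arm, and 80 × 0.80 = 64 evaluable. At 32 per arm √(n/2) = 4, so the noncentrality is 2.0, 2.4, 2.8 and 3.2 for the four effects.

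| Recruited | Dropout | Evaluable per arm | d = 0.50 | 0.60 | 0.70 | 0.80 |
|---|---|---|---|---|---|---|
| 80 | 20% | 32 | 50.4% | 65.6% | 78.7% | 88.3% |
| 80 | none | 40 | 59.8% | 75.5% | 87.1% | 94.2% |
| 160 | 20% | 64 | 80.1% | 92.0% | 97.6% | 99.4% |

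The smallest effect with 80% power is d of about 0.71 at 32 per arm and about 0.63 at 40 per arm. A normal approximation gives 51.6% in place of 50.4%, so the result does not depend on the method.

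**Step 4: what the completion rule could mean.** Section 1.3 C counts completers. From the two-arm columns without dropout, the minimum could be anything from 2 × 26 = 52 (d = 0.80) to 2 × 64 = 128 (d = 0.50).

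**Step 5: the anesthesia columns.** At d = 0.50 with dropout they show 160 per treatment type, or 2 × 160 = 320 in total, twice the top of the stated range. No anesthesia subgroup appears in the objectives, the endpoints or the analysis.

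**The case against.** The best defence is that Section 4.3 never says where its range comes from. The upper end is correct for two arms at d = 0.50, three of the four implied totals (86, 114, 160) lie inside the range, and 80 exceeds the fourth (66). It could be a loose planning range. This has some force: reuse of per-arm figures is an inference. It remains the more likely explanation, because 80 matches no two-arm total and does match the per-arm cell of the same row that contains 160.

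A reader might also infer that the protocol claims 80% power at d = 0.50 for 80 patients and that the claim is false. The document does not support that. It adopts no row, and at d = 0.80 a total of 80 gives 88% after dropout. The 50% figure combines the smallest listed effect, the bottom of the range and full dropout. Nor would a null result at 80 tell us nothing: with 32 per arm the 95% interval has a half-width of about 2.0 × √(2/32) = 0.50 SD, so a difference near zero would still argue against effects of 0.7 to 0.8.

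Finally, a reader might infer that the open range invites a test at 80 and another at 160, inflating the type I error. No interim comparison is described: Section 1.3 C ends the study on a count of completers, and Section 6.1 describes a single comparison. That argument should not be made from this document.

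**Conclusion.** The point holds as an inconsistency between Sections 1.3 C, 1.5 and 4.3. The table's two-arm arithmetic is correct. What is wrong is that the stated total permits a trial of 80, which misses the 80% power of the table's own rows for d = 0.50, 0.60 and 0.70. The shortfall is about 30 percentage points at d = 0.50 and 14 at 0.60, but only about 1 at 0.70; at d = 0.80 there is none. Without dropout, the shortfall at d = 0.50 is still about 20 points.

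These figures rest on a two-sided 0.05 test, 1:1 allocation and the table's 20% dropout applied to the number recruited. The size of the shortfall depends on which effect the trial is meant to detect, which the protocol does not say. Section 1.4 reports no local preliminary data from which to infer it. That the per-arm figures were reused is probable but not proven; the mismatch stands either way.

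**What to change.** Choose one design effect and one total, and state the same pair in Sections 1.3 C, 1.5 and 4.3. Two options are consistent with the table:

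- **160 in total:** 80 per arm, 64 evaluable per arm after 20% dropout, 80% power for d = 0.50. This is already the top of the stated range.
- **80 in total:** 40 per arm, 32 evaluable per arm after 20% dropout, with the claim restated as 80% power for d of about 0.71 or more and about 50% power for d = 0.50.

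In Section 1.3 C, replace the reference to an unspecified minimum with the chosen number, and say whether it counts patients recruited or patients completing. State that the test is two-sided and the allocation 1:1, if that is intended. Remove the anesthesia-subgroup columns from Section 1.5, or describe and justify the comparison they are meant to power.

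The cost is protocol wording in three sections. Neither option needs patients beyond the range already stated, although the first commits the team to twice the present lower end.
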